6.3.2 Blood volume

Blood volume drawn will be: 61 samples x 2 ml = 122 ml for intervention visits of rapid insulin alone and rapid insulin and pramlintide.

Blood volume drawn will be: 64 samples x 2ml = 128ml for the intervention visit of regular insulin and pramlintide.

Note that extra samples might be drawn as required.

6.4 Intervention Criteria

6.4.1 Treatment of Hypoglycemia

Hypoglycemia is very common in real life in patients with type 1 diabetes. The JDRF CGM trial reported hypoglycemia <3.3 mmol/L in about 9% of the nights, half of them lasting at least one hour and quarter of them lasting at least two hours [10]. Patients also experience symptomatic hypoglycemia around 2.7 times per week [11]. Moreover, hypoglycemia remains underestimated with up to 60% of events remaining unrecognized [12]. Therefore, ideally, we would like to observe the differences in hypoglycemia between the interventions, especially that hypoglycemia is identified as the major limiting factor to achieve glycemic goals [13]. This can be best achieved if the investigators do not intervene during the study, replicating home settings as much as possible. However, despite the importance of observing hypoglycemia events and their duration as they would happen spontaneously in real life, research staff will need to intervene in the event of hypoglycemia for safety reasons.

By default, treatment of hypoglycemia will be based on plasma glucose levels. However, in the event plasma glucose measurements are unavailable, sensor or capillary glucose values will be used to determine if the patient requires a treatment.

The following guidelines will be followed for the treatment of hypoglycemia.

- If glucose levels are < 3.3 mmol/L and associated with symptoms, the patient will self-administer 16g of oral carbohydrates to treat hypoglycemia. Glucose levels will be measured again in 15 minutes and the patient will self-administer another 16g of carbohydrates if glucose level is not > 3.3 mmol/L.
- If glucose levels are < 3.0 mmol/L irrespective of symptoms, the patient will self-administer 16g of oral carbohydrates to treat hypoglycemia. Glucose levels will be measured again in 15 minutes and the patient will self-administer another 16g of carbohydrates if glucose level is not > 3.3 mmol/L.

6.4.2 Treatment of Hyperglycemia

By default, treatment of hyperglycemia will be based on plasma glucose levels. However, in the event that plasma glucose measurements are unavailable, sensor glucose or capillary glucose values will be used to determine if patient requires a treatment.

If glucose level >18.0 mmol/L for two consecutive samples or if capillary glucose at the start/end of the study is >18 mmol/L, blood ketones will be checked.

- if ketones < 1.5 mmol/L (negative) and glucose level is maintained > 18.0 mmol/L over the next 2 hours:
 - The patient will be asked to change their infusion set.
 - Blood ketones will be re-assessed at the 2-hour mark (± 10 minutes). The hyperglycemia procedures will be repeated based on the results.
- if ketones < 1.5 mmol/L (negative) and glucose level falls below 18.0 mmol/L over the next 2 hours, no additional measures will be taken.
- if ketones < 1.5 mmol/L (negative) at the end of the study, the patient will be reminded by the research staff to take a correction bolus as per their standard practice.
- if ketones > 1.5 mmol/L (positive):
 - The study will be stopped, however the patient will not be discharged until acceptable blood ketone levels (lower than 1.5 mmol/L) are reached.
 - Additional insulin of 0.1 units/kg will be administered via a syringe by the research nurse. This step will be repeated every 2 hours (± 10 minutes) until blood ketones are corrected.

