6.4.3 Stopping Criterion

The study will be stopped at the discretion of the investigators in the following circumstances:

- If no glucose measurements (plasma, capillary, or sensor glucose) are obtained for more than 2 hours during the 24-hour intervention visit.

7 Statistical Analysis

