7.1 Study Endpoints

7.1.1 Primary comparisons

Percentage of time of glucose levels spent in target range (defined to be between 3.9 and 10.0 mmol/L). The following comparisons will be done:

- i) Fast-acting insulin-plus-pramlintide closed-loop delivery vs. fast-acting insulin-alone closed-loop delivery;
- ii) Regular insulin-plus-pramlintide closed-loop delivery vs. fast-acting insulin-alone closed-loop delivery.

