7.2 Sample Size and Power Calculations

The power calculations aim to compare the effects of the interventions on the primary endpoint (time in target range), made at the $\alpha=0.05/2$ significance level: **i)** fast-acting insulin-alone closed-loop delivery and fast-acting insulin-plus-pramlintide closed-loop delivery; **ii)** fast-acting insulin-alone closed-loop delivery and regular insulin-plus-pramlintide closed-loop delivery.

The anticipated difference in time in target range was estimated from Weinzimer et al [6]. In that study, pramlintide increased the time spent in target range by 4%. In our study, we infuse pramlintide during the night too, and we anticipate that will improve glucose control even more. We anticipate that the insulin-plus-pramlintide closed-loop delivery will increase the percentage of time spent in target range by 7% (SD=10%) compared to the insulin alone closed-loop system. The standard deviation of the differences in the percentage of time in target range is estimated from our previous studies. It has always been between 9% and 11% for all comparisons that we usually make (sensor-augmented pump therapy, single-hormone artificial pancreas, and dual-hormone artificial pancreas).

Using the typical sample size formula for paired t-test, we calculated that 22 participants would provide 80% power at the 2.5% (0.05/2) significance level to detect differences between the interventions in the primary comparison. To account for anticipated drop-outs, technical problems, and remaining uncertainty in power calculations, 28 participants will be recruited.

Participants who do not complete one fast-acting insulin-alone closed-loop intervention and at least one insulin plus-pramlintide closed-loop intervention will be replaced in the enrollment process, will not be included in the analysis, and will not count toward the recruitment goal.

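### Section 7.2, read plainly, can exclude participants because a visit was stopped for ketones under 6.4.2, and the plan does not say how a stopped visit enters time in range

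*Combined protocol and SAP*

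**What the plan says.** **The stop.** Section 6.4.2 calls for a ketone check "If glucose level >18.0 mmol/L for two consecutive samples or if capillary glucose at the start/end of the study is >18 mmol/L". A result above 1.5 mmol/L counts as positive, and then "The study will be stopped, however the patient will not be discharged until acceptable blood ketone levels" are reached. I take the study here to mean the visit, since the sentence goes on to discharge. Additional insulin is given after the stop until ketones are corrected. A negative result does not end the visit: the branch that begins "if ketones < 1.5 mmol/L (negative) and glucose level is maintained > 18.0 mmol/L over the next 2 hours" continues with other measures and a repeat ketone check.

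**The stopping section.** Section 6.4.3 opens with "The study will be stopped at the discretion of the investigators in the following circumstances" and lists one circumstance: "If no glucose measurements (plasma, capillary, or sensor glucose) are obtained for more than 2 hours during the 24-hour intervention visit". The ketone stop is not listed there.

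**The endpoint.** Section 7.1.1 gives the primary endpoint as "Percentage of time of glucose levels spent in target range (defined to be between 3.9 and 10.0 mmol/L"). It sets no minimum observed time and no denominator for a shortened visit.

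**The analysis set.** Section 7.2 says of "Participants who do not complete one fast-acting insulin-alone closed-loop intervention and at least one insulin plus-pramlintide closed-loop intervention" that they are replaced, are left out of the analysis and do not count toward recruitment. The word *complete* is not defined. Section 7.4 specifies a linear mixed model and does not mention partial or missing visits.

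**The concern.** The ketone stop can only follow glucose far above the upper limit of the target range, 10.0 mmol/L. Whether a visit runs its full course therefore depends partly on the variable being analysed. If completion is also a condition of being analysed, data are lost because of the outcome.

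The loss is also uneven between arms. The rule in 7.2 works per participant and requires the control visit, so a stopped control visit would remove that person from both primary comparisons, whatever happened at the two pramlintide visits. A stopped pramlintide visit does not remove the person if the other pramlintide visit was completed, and nothing says what then happens to the stopped visit's own data. Losing poor control visits makes control look better; losing poor pramlintide visits makes pramlintide look better. Replacement restores the headcount, so the final sample size would not reveal the loss.

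The mixed model does not settle the matter. It can use a participant's remaining visits, but if the stopped visit contributes no value, the model has not conditioned on the glucose that caused the stop.

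**Working it through.** **1. The plan's own figure.** Inputs from 7.2: difference 7 points, SD of differences 10, significance level 0.025 per comparison, 80% power, paired t-test. Sidedness is not stated; two-sided is assumed. With the noncentral t distribution, n = 22 gives 80.0% power, so the stated 22 reproduces. At n = 28 power is 90.1%. The point below concerns which data are analysed and leaves this calculation untouched.

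**2. What happens to a stopped visit, case by case.**

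| Visit stopped for ketones | Result under 7.2 if a stopped visit is not complete | Stated in the plan? |
|---|---|---|
| Control | Participant excluded and replaced; both pramlintide visits lost too | Follows from 7.2 on the plain reading |
| One pramlintide visit, other pramlintide visit and control completed | Participant stays | Fate of the stopped visit's data not stated |
| Both pramlintide visits | Participant excluded and replaced | Follows from 7.2 on the plain reading |
| Any visit, if its partial data are used | Time in range over an unspecified denominator | Not stated |

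**3. Truncation.** Assume the primary endpoint uses the 8:00 to 8:00 window given for the secondary endpoints in 7.1.2. A visit stopped at 14:00, taken as an example, has 6 of 24 hours, or 25%. If a fraction p of those 6 hours was in range, the visit scores p on observed time, but p × 6/24 = 0.25p if the remaining 18 hours count as out of range. The plan does not choose between these.

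**4. Size if stopped pramlintide visits are dropped (illustration).** The documents give neither a stop rate nor glucose values for such visits. Assume that k stopped visits in one pramlintide arm each lie 30 points below the same person's control visit, and that every other pair shows +7.

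True mean difference = [7(n − k) − 30k] / n. The mean after dropping is 7, so the overstatement is 37k/n.

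For k = 1, n = 28: (27 × 7 − 30)/28 = 159/28 = 5.68. For k = 1, n = 22: (21 × 7 − 30)/22 = 117/22 = 5.32.

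| k | True mean, 28 pairs | Overstatement | True mean, 22 pairs | Overstatement |
|---|---|---|---|---|
| 1 | 5.68 | 1.32 | 5.32 | 1.68 |
| 2 | 4.36 | 2.64 | 3.64 | 3.36 |
| 3 | 3.04 | 3.96 | 1.95 | 5.05 |

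**5. Range for the assumed gap.** Alternatively, hold the true mean over all 28 pairs at 7 and let each dropped pair lie g points below it. The shift is kg/(28 − k). For g from 20 to 50:

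- k = 1: 20/27 to 50/27 = 0.7 to 1.9 points
- k = 2: 40/26 to 100/26 = 1.5 to 3.8 points
- k = 3: 60/25 to 150/25 = 2.4 to 6.0 points

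If the dropped visits are control visits, with pair differences g points above the mean, the estimate moves down by the same amounts.

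**The case against.** **Completion is undefined.** A reader might infer that every stopped visit is incomplete and leaves the primary endpoint. The documents do not say so. Section 7.2 sets a rule for participants, not visits, and a mixed model could in principle take a partial visit. This stands for the single stopped pramlintide visit, whose handling is simply unspecified. It is weaker for the control visit: on the ordinary meaning of the word, a 24-hour visit halted partway is not completed, and 7.2 then excludes the person.

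**Which visits are affected.** A reader might also infer that the visits with the worst glucose are removed in general. That is too broad. Visits above 18.0 mmol/L with negative ketones continue. A positive check at the end costs little or no data. A positive check at the start precedes closed-loop control, which 6.1.1 begins at 7:40 or 8:00, so it reflects the optimization period and not closed-loop time in range. This stands.

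**Rarity.** These are supervised 24-hour visits with adjustments every 10 minutes after at least 10 days of optimization. Three stops in 28 would be 11% of visits in an arm, and nothing in the documents supports or excludes that. The figures show that a bias is possible, not that it is likely. This stands.

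**Adverse events.** It is tempting to say that ketosis would go unrecorded because 10.2 names only severe hypoglycemia. The general definition in 10.1 can capture it. What is missing is a planned count of stopped visits by arm.

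**6.4.2 against 6.4.3.** A reader might call these contradictory. They are not: 6.4.3 does not claim to be exhaustive, and an unconditional ketone stop can operate beside a discretionary one for missing glucose. A cross-reference is all that is lacking.

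**Retained data have their own problem.** Sensor glucose after the stop reflects the rescue insulin and could credit the arm with time in range that the closed loop did not produce. This is a fair objection to using that value alone.

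**Conclusion.** The concern holds in a limited form. Read plainly, 7.2 excludes a participant whose control visit is stopped for ketones, and that exclusion depends on both the primary outcome and the arm. For a single stopped pramlintide visit, and for the truncated percentage of any stopped visit, the plan gives no rule.

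The size cannot be determined from the documents. Under the stated assumptions, each dropped pramlintide visit overstates the difference by about 1.3 points (28 pairs) to 1.7 points (22 pairs), against an anticipated effect of 7. The 30-point deficit and the number of stops are assumptions. The documents do not support a claim that the result will be biased in favour of pramlintide: the direction depends on which arm has the stops, and there may be none. This is a worthwhile, inexpensive improvement for a possibly rare event, best settled before any stopped visit forces a choice made with the data in view.

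**What to change.** - **7.2 and 7.4:** state that a visit stopped under 6.4.2 after closed-loop control has begun counts as that arm's visit, and that neither the visit nor the participant is excluded or replaced because of the stop.
- **Primary value:** derive time in range from the glucose data available, including the sensor already worn, and state the denominator. Section 6.3.1 already lets the study proceed on sensor values when plasma glucose is unavailable.
- **Sensitivity analysis:** prespecify one that counts time after the stop as out of range, reported beside the primary result because sensor glucose after the stop reflects rescue insulin.
- **Start check:** handle stops before closed-loop control separately and say how, since such a visit has no closed-loop data to attribute to the arm.
- **7.1.2:** report the number of stopped visits by arm and reason.
- **6.4.2 and 6.4.3:** cross-reference them so that the stopping events are listed consistently, with each marked as automatic or discretionary.

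The cost is a few sentences in 6.4, 7.1.2, 7.2 and 7.4, with no new device or staff. No clinical threshold or treatment is questioned.

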6.4.3 Stopping Criterion

The study will be stopped at the discretion of the investigators in the following circumstances:

- If no glucose measurements (plasma, capillary, or sensor glucose) are obtained for more than 2 hours during the 24-hour intervention visit.

7 Statistical Analysis

7.1 Study Endpoints

7.1.1 Primary comparisons

Percentage of time of glucose levels spent in target range (defined to be between 3.9 and 10.0 mmol/L). The following comparisons will be done:

- i) Fast-acting insulin-plus-pramlintide closed-loop delivery vs. fast-acting insulin-alone closed-loop delivery;
- ii) Regular insulin-plus-pramlintide closed-loop delivery vs. fast-acting insulin-alone closed-loop delivery.

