4.1 Trial Design

This study is a randomized, three-way, crossover trial to compare the efficacy of **i)** fast-acting insulin-plus-pramlintide closed-loop delivery, **ii)** regular insulin-plus-pramlintide closed-loop delivery, and **iii)** fast-acting insulin-alone closed-loop delivery in regulating glucose levels over a period of 24 hours in a study on adults in inpatient settings. Insulin (fast-acting and regular) and pramlintide are given with fixed ratio (6 µg of pramlintide for each unit of insulin).

Before each 24-hour intervention visit, the participant's insulin therapy (basal rates and insulin-to-carbohydrate ratios) will be optimized for a minimum of 10 days, with a target of 14 days. If a participant is randomized to either rapid or regular insulin-plus-pramlintide arms, pramlintide will be infused using a second pump at a fixed ratio for a minimum of 10 days, and insulin therapy will be optimized. Regular insulin will replace participant's usual insulin and will be initiated for a minimum of 10 days, and insulin therapy will be optimized.

There will be a wash-out period of 0 to 42 days between the three intervention arms (termination of 24-hr intervention and start of next optimization period).

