7.1.2 Secondary endpoints and comparisons

1. Percentage of time of glucose levels spent in target range, comparing fast-acting insulin-plus-pramlintide closed-loop delivery vs. regular insulin-plus-pramlintide closed-loop delivery.
2. Percentage of time (8:00-8:00) of glucose levels spent:
 - a.* between 3.9 and 7.8 mmol/L; *b.* between 3.9 and 10 mmol/L; *c.* below 3.9 mmol/L; *d.* below 3.3 mmol/L; *e.* below 2.8 mmol/L; *f.* above 7.8 mmol/L; *g.* above 10 mmol/L; *h.* above 13.9; *i.* above 16.7 mmol/L.
3. Percentage of overnight time (23:00-8:00) of glucose levels:
 - a.* between 3.9 and 7.8 mmol/L; *b.* between 3.9 and 10 mmol/L; *c.* below 3.9 mmol/L; *d.* below 3.3 mmol/L; *e.* below 2.8 mmol/L; *f.* above 7.8 mmol/L; *g.* above 10 mmol/L; *h.* above 13.9; *i.* above 16.7 mmol/L.
4. Standard deviation of glucose levels as a measure of glucose variability.
5. Total insulin delivery.
6. Total pramlintide delivery.
7. Mean glucose level during: *a.* the overall study period; *b.* overnight period.
8. Mean insulin concentration.
9. Mean glucagon concentration.
10. Mean amylin concentration.
11. Number of participants experiencing hypoglycemia requiring oral treatment during: *a.* the overall study period; *b.* the night.
12. Gastrointestinal symptoms during the treatment optimization (i.e., the minimum 10 days prior to the 24-hour closed-loop visits) and during the 24-hour closed-loop visits.

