7.3 Level of Significance

5% significance threshold will be used to declare statistical significance. Bonferroni correction will be used for the two primary comparisons. No formal correction will be applied for the secondary comparisons.

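### Does listing time in 3.9 to 10 mmol/L again as secondary item 2b give the primary result a second, uncorrected significance threshold?

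*Combined protocol and SAP*

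**What the plan says.** All references are to the combined protocol and SAP.

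- Section 7.1.1 defines the primary endpoint as "Percentage of time of glucose levels spent in target range (defined to be between 3.9 and 10.0 mmol/L") and names two comparisons. The first is "Fast-acting insulin-plus-pramlintide closed-loop delivery vs. fast-acting insulin-alone closed-loop delivery"; the second sets regular insulin plus pramlintide against the same control. It gives no clock window.
- Section 7.1.2, item 1, takes the same endpoint for the remaining pair, the two pramlintide arms. Item 2 is "Percentage of time (8:00-8:00) of glucose levels spent" in nine bands, of which 2b is "between 3.9 and 10 mmol/L". Item 3 repeats the nine bands overnight. Items 2 and 3 name no treatment pair.
- Section 7.3: "5% significance threshold will be used to declare statistical significance. Bonferroni correction will be used for the two primary comparisons". It then adds: "No formal correction will be applied for the secondary comparisons".
- Section 7.2 reports the sample size: "we calculated that 22 participants would provide 80% power at the 2.5% (0.05/2) significance level". It names the same two pairs as Section 7.1.1.
- Section 4.1 describes the comparison as one of efficacy "in regulating glucose levels over a period of 24 hours". Section 6.1.1 (initial procedures) starts the closed loop at 7:40 in the regular-insulin arm and at 8:00 in the others.

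**The concern.** Item 2b has the same metric and glucose limits as the primary endpoint, and its window matches the 24 hours of Section 4.1. No section gives the two a different glucose source. Item 1 already covers the third pair, so 2b seems to add only a second listing of the primary contrasts, this time under a heading where no correction applies.

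If 2b were tested as an ordinary secondary comparison, a p-value between 0.025 and 0.05 would fail under Section 7.1.1 and pass under Section 7.1.2. The second statement would amount to the trial's primary claim, a gain in time in range, without the Bonferroni split that protects it. With two comparisons, the summed error would be 2 × 5% = 10% instead of 2 × 2.5% = 5%.

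**Working it through.** **Inputs.** From Section 7.2: expected difference 7 points, SD of the paired differences 10 (range 9 to 11), power 80%, 0.05/2 per comparison, 22 evaluable and 28 recruited, and a difference of 4 points in the cited earlier study. Assumed: two-sided tests (the plan does not say, but this reproduces its 22) and a paired t-test in place of the mixed model of Section 7.4.

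**1. The plan's own figure.** Standardised difference 7/10 = 0.7.

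- Normal formula: ((2.241 + 0.842)/0.7)² = 19.4. With the usual small-sample term 2.241²/2 = 2.51, this becomes 21.9, so 22.
- Exact non-central t: 22 participants give 80.0% power at 2.5% and 21 give 77.7%. At 5% only 19 would be needed.

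The stated 22 therefore belongs to 2.5%, which identifies the threshold on which the primary comparisons were designed.

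**2. The zone of disagreement.** The smallest significant mean difference is t × SD/√n, here with SD 10.

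| n | SD/√n | at 5% | at 2.5% |
|---|---|---|---|
| 22 | 2.132 | 2.080 × 2.132 = 4.43 | 2.414 × 2.132 = 5.15 |
| 28 | 1.890 | 2.052 × 1.890 = 3.88 | 2.373 × 1.890 = 4.49 |

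For n = 28, the zone is 3.49 to 4.04 with SD 9 and 4.27 to 4.93 with SD 11.

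**3. Chance that one comparison falls in the zone** (power at 5% minus power at 2.5%, SD 10).

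| True difference | n = 22 | n = 28 |
|---|---|---|
| 0 | 2.5% | 2.5% |
| 4 | 43.3% − 31.7% = 11.6% | 53.2% − 41.2% = 12.1% (unrounded powers) |
| 7 | 87.9% − 80.0% = 7.9% | 94.6% − 90.1% = 4.5% |

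**4. Two comparisons, no true effect, n = 28.** With a correlation of 0.5 assumed from the shared control, the simulated chance of at least one significant result is 4.6% at 2.5% each and 9.0% at 5% each. Correlation 0.3 gives 4.8% and 9.4%; correlation 0.7 gives 4.4% and 8.5%. The chance that neither comparison passes as primary but at least one passes as 2b is 4.4% with no effect, 12.3% if both true differences are 4, and 1.8% if both are 7.

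**5. Does the plan state 5% for these contrasts?** The 5% comes from joining the general threshold in Section 7.3 with the absence of a secondary correction; it is not printed beside 2b. Against that inference stand three specific statements. Section 7.3 ties the correction to the two primary comparisons, Section 7.1.1 defines those by endpoint and pair, and Section 7.2 gives 0.05/2 for the same pairs. A contrast that meets the definition of a primary comparison remains one when its glucose band reappears in a list. The excess in step 4 arises only if all three statements are set aside.

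**6. Is 2b the same quantity?** For the first pair, yes on a 24-hour reading, since both arms start at 8:00. For the second pair it depends on the primary window. Including 7:40 to 8:00 in the regular-insulin arm adds 20 minutes to 1,440. The percentage then moves by at most 20/1,460 = 1.4 points per person. Someone with 70% in range (1,008 minutes) would move to 1,028/1,460 = 70.4% or 1,008/1,460 = 69.0%. The 8:00-8:00 window in item 2 and the 24 hours in Section 4.1 point to the common window.

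**7. What would deletion gain?** The share below 3.9, the share in 3.9 to 10 and the share above 10 add up to 100%. Items 2c (below 3.9) and 2g (above 10) would stay, uncorrected. When little time is spent low, 2g is almost the mirror image of the primary endpoint. Anyone inclined to restate a missed primary result as a secondary success could use 2g just as well.

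**The case for a change.** The strongest case for a change is that a plan should settle such points before results are known, and that the remedy is nearly free. The list is headed as endpoints and comparisons, Section 7.3 gives secondary comparisons a significance rule, and Section 7.4 models the continuous endpoints without marking 2b as descriptive. If the true effect is nearer the 4 points of the cited study than the hoped-for 7, the chance of a result in the disputed zone is about 12% per comparison, which is not negligible. The primary window is also unstated beside a secondary item that states one.

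Much of this stands as description: the duplication is real, the arithmetic is right, and a cross-reference would be tidier. What does not stand is the step from a repeated row to a second threshold. The probabilities in steps 3 and 4 measure how often the two readings would differ, not how often the plan followed as written would err. On the window, a 20-minute difference in one arm concerns how the endpoint is defined, not which alpha applies, and item 2 already indicates the reading an analyst would take.

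**Conclusion.** The concern does not call for a change. Item 2b is a redundant row in a list of glucose bands, written once for 24 hours and once overnight. The plan fixes 2.5% for time in range in both primary comparisons through Sections 7.1.1, 7.2 and 7.3, and the 22 participants reproduce at that level with 80.0% power. Followed as written, the family error for the primary claim stays within 5% (about 4.6% with correlation 0.5). The 9.0% alternative would require the investigators to disregard their own Bonferroni rule, and deleting 2b would not prevent that while 2g remains.

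The sensible handling is to show the 3.9 to 10 row in the results table as the primary result, judged at 2.5%. This rests on two-sided tests, an SD near 10 and the paired t-test as a stand-in for the mixed model. An approximate mixed-model check with 52 degrees of freedom, 28 participants and SD 10 gives cut-offs of 3.79 and 4.36 points, close to the 3.88 and 4.49 above. The conclusion does not turn on those figures, because it depends on which threshold the plan assigns to the primary comparisons, and that is 2.5%.
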